In addition, majority of cases of DILI in the published clinical and genetic studies have been enrolled retrospectively; hence, the data set is reliant on clinical investigations and the setup of health services which are incomplete. In addition, the majority of the studies have used healthy populations as control groups (rather than those exposed to the drugs). Despite the discovery of genetic factors such as the association of specific HLA genotype with DILI, a low positive predictive value of the genotype in predicting DILI is limiting its use in clinical practice [8,9]. Age, smoking, metabolic syndrome, co-morbidity and other yet unidentified factors may generate an environment of oxidative stress that contributes to DILI. Therefore, we need 'in-depth phenotyping' together with data from an exposed control group to develop refined algorithms incorporating drug-related factors, host genetic and environmental risk factors that would enable us to pre-empt DILI. Deeply phenotyped cohorts with biological samples are essential for the development and validation of novel diagnostic/ prognostic markers [10].

STUDY OBJECTIVES AND PURPOSE

Purpose

The purpose of this study is to set up an international interdisciplinary consortium to obtain a better understanding of the mechanisms underlying drug-induced liver injury (DILI) and to develop methods of preventing DILI and its consequences. The consortium including the clinicians and scientists from European countries covering a wide area of expertise will allow the development of mature hypotheses that can be tested using a robust study design. The consortium will facilitate the development of strong translational research proposals based on our hypothesis.

Primary Objective

To, collect, store and catalogue biological samples and clinical data, to form a large international patient/control cohort available for subsequent detailed analysis by consortium members which can also be used in current and future epidemiologic and mechanistic studies.

Proposal Aims:

We hypothesise that the severity of DILI is determined by factors that modulate cellular response to oxidative stress and the transition of adaptive response to the development of serious DILI can be recognised by a combination of markers that reflect the balance

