between pro- and anti-inflammatory responses to oxidative stress. So, we will develop a panel of markers that assess the severity of DILI. As the prospective in-depth phenotyped DILI cohort and controls are being recruited, the network infrastructure can also support any evaluation and validation of novel tests with potential application in DILI.

There are no evidence-based treatments for DILI; rarity of the condition and heterogeneity of the manifestations prevents the conception and successful completion of clinical trials. Multicentre Pro-Euro-DILI registry will provide both the infra-structure to conduct clinical trials, and also a sufficient number of well characterised patients to evaluate the efficacy of novel anti-cholestatic agents in the resolution of DILI [11].

STUDY PLAN

Biomarker Identification & Evaluation:

Participants will be asked to give consent for their anonymised samples and anonymised data to be stored and used for the purposes of this International study and to be stored in a research tissue bank and used for future research.

Clinical and phenotypic data, outlined in the CRF, will be collected by the study centre. Each participating study centre will collect and process biological samples as per SOP. Samples will be kept at -80°C and shipped in regular batches to the NIHR Nottingham Biomedical Research Centre (BRC). To determine other biomarkers of interest, samples will be analysed by researchers at Nottingham or collaborating institutions or by commercial suppliers.

Upon completion of the study, where consent is given, samples will be transferred to an appropriate ethically approved research tissue bank and made available for ethically approved research programs with approval of partners as specified in collaboration agreements. Any samples stored at Nottingham University Hospitals NHS Trust will be transferred to the custodianship of University of Nottingham (HTA Licence No. 12265; Designated Individual: [name]) and stored in the NDDC-BRU Research Tissue Bank for up to 10 years.

Outline of Laboratory Analyses

Appendix 1 gives an overview of the patient data and clinical analyses to be included (where possible) which are part of clinical care.

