Healthy Control Group:

Adults who are exposed to the same drugs (as those responsible for DILI) without developing DILI will be identified. The Chief Investigator will access hospital pharmacy databases to identify patients taking specific drugs of interest. Then patients exposed to particular drugs without developing DILI will be invited to participate in the study as a control group. In the UK this will be done at the Nottingham site initially, extending to other sites where appropriate.

We will also advertise through BRC website (https://nddcbru.org.uk/pro-euro-dili) (appendix 2 shows screen shot) and social media pages (Facebook and Twitter) to invite people who have taken the particular drugs to contact us if they are interested in participating in the study (as control group).

A proportion of patients who are suspected to have DILI and enrolled as cases will be found to have an alternative explanation for their clinical manifestation found on subsequent investigation. The data and samples taken from these patients will be retained in the study and termed 'symptomatic controls' for analysis purposes. Sample and data collection will be continued in line with confirmed DILI participants.

INFORMED CONSENT

The process for obtaining participant informed consent will be in accordance with the REC guidance, and Good Clinical Practice (GCP) and any other regulatory requirements that might be introduced. Since DILI symptoms are acute and patients often present in emergency departments with sudden onset of severe symptoms, a long period (e.g. 24h) to consider consent is often difficult to provide in order to recruit patients while symptomatic and without asking patients to make additional hospital visits. Therefore, where appropriate, patients will be given a reasonable time period (ideally1 hour without disturbance), to read the patient information sheet and consider enrolment before being approached for consent by the research team. Appropriate steps will be taken to ensure that the patient is able to discuss participation in the study with those not involved in the research. The investigator or

Pro-Euro-DILI Registry Protocol Page 15 of 32

their nominee and the participant or other legally authorised representative shall both sign and date the Consent Form before the person can participate in the study.

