All routine laboratory analysis will be done by appropriate hospital as part as normal patient care. Blood will be processed for storage of serum and plasma as outlined in the SOP. Data and all appropriate documentation will be stored for a minimum of 25 years after the completion of the study, including the follow-up period.

We will collate detailed and comprehensive data using an electronic case report form (eCRF) to achieve in-depth phenotyping.

The procedure for data removal in the event of withdrawal of consent is described on pg 25.

Statistical Analyses

Researchers will be blinded to patient type/group being investigated – samples will be anonymized and labelled only with study ID code. Study groups will be compared using T-tests and non-parametric testing to identify biomarkers which distinguish DILI.

STUDY MANAGEMENT

The day-to-day management of the study will be co-ordinated through Nottingham Digestive Diseases Centre and NIHR Nottingham Biomedical Research Centre.

SPONSOR

Nottingham University Hospitals NHS Trust will act as the main sponsor for UK based sites for this study. Delegated responsibilities will be assigned to the NHS trusts taking part in this study.

FUNDING

Participant stipends and payments

Participants will not be paid to participate in the study. Travel expenses will be offered for any hospital visits in excess of usual care.

AUDITS

The study may be subject to inspection and audit by Nottingham University Hospitals under their remit as sponsor and other regulatory bodies to ensure adherence to GCP and the NHS Research Governance Framework for Health and Social Care (2nd edition).

STUDY CONDUCT

Study conduct will be subject to systems audit for inclusion of essential documents; permissions to conduct the study; CVs of study staff and training received; local document control procedures; consent procedures and recruitment logs; adherence to procedures defined in the protocol (e.g. inclusion / exclusion criteria, timeliness of visits); accountability of study materials and equipment calibration logs.

STUDY DATA

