We will disseminate findings to the public and provide study information and updates on our website and newsletter and at public engagement events such as the BRC open day. We held a meeting of representatives from the BRC patient advisory group in June 2018 to provide feedback about study dissemination. In particular advice was provided to develop strategies for patient engagement and publicity to improve recruitment. As a consequence we developed improved patient information and website. The advisory group were also supportive of our plan to extend study through securing funding via a European consortium in order to develop biomarker tools for use in clinical care. They felt that the purpose of a biorepository would be to share samples and develop collaborations worldwide since this is a rare condition and this would enable specialize analyses to be included.

REFERENCES

- 1. de Abajo FJ. et al., Br J Clin Pharmacol. 2004;58:71-80.
- 2. Sgro C. et al., Hepatology. 2002;36:451-5.
- 3. Björnsson ES. et al., Gastroenterology. 2013;144:1419-25.
- 4. Aithal GP. et al., Clin Pharmacol Ther. 2011;89:806-15.
- 5. Marie-Lea Gauci et al., 2018 J Hepatology; 69 j 547–558
- 8. Aithal GP. Nat Rev Rheumatol. 2011;7:139-50.
- 9. Lucena MI. et al., Gastroenterology. 2011;141:338-47.
- 11. Wree A. et al., Digestion. 2011;84:54-9.
- 13. Foureau, D. 2014, Clinical and experimental immunology 180:40-51.
- 14. Taubert R. 2014 J Hepatology 61;1106-1114.
- 15. Benesic A et al. Gut. 2015; 0,1-9.
- 16. Kay AW et al. Methods Mol Biol. 2016; 1441: 13-26.

Pro-Euro-DILI Registry Protocol Page 29 of 32

APPENDICES:

	Day 0	Day 1-6	Day 2- 6	Day 7 -15	Day 30 ±20	Day 90 ±30	Day 180 ±90
	Visit 1#	Visit 1B Optional [§]	Visit 1C Optional [§]	Visit 2	Visit 3	Visit 4 Optional §§	Visit 5 Optional §§§
Inclusion/Exclusion criteria (LFTs reviewed after visit completed)	Х						
Medical history comorbidity	х						
current medical condition	Х	Х	Х	Х	Х	Х	Х
Demography inc pregnancy and ethnicity	Х						
Body height and weight	Х					Х	Х

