Drug history in past 6 months or longer, including OTC, herbal, dietary supplement, recreational drugs (include at least 10 most recently taken drugs).Subsequent visits only need to document new drugs	х	х	х	х	х	х	x
Smoking history	Х						
Alcohol, quantitative assessment	Х						
Viral hepatitis screen (where appropriate for clinical care)	Х						
Autoantibody* screening (where appropriate for clinical care)	Х				(X)**		
Liver ultrasound(where appropriate for clinical care)	Х						
Liver ultrasound(where appropriate for clinical care)	Х						
Blood sample collection (see separate SOP for detail) up to 80 ml in total inc clinical bloods	Х	х	Х	Х	Х	х	х
Urine sample collection if possible	Х	Х	Х	Х	Х	Х	х
Liver biopsy tissue where done as part of clinical care (surplus tissue only)	х						
Stool sample collection if possible	Х	Х	Х	Х	Х	Х	Х

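### The only biomarker comparison the protocol names is unadjusted, yet the protocol ties host factors to both oxidative stress and DILI and does not match non-symptomatic controls on them

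*Protocol*

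**What the plan says.** Protocol, Statistics and Data Analysis, Statistical Analyses: "Study groups will be compared using T-tests and non-parametric testing to identify biomarkers which distinguish DILI". The same paragraph provides for blinding of the researchers to patient group. It mentions no model, covariate, stratum or matched analysis.

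Protocol, Rationale for current study: "Age, smoking, metabolic syndrome, co-morbidity and other yet unidentified factors may generate an environment of oxidative stress that contributes to DILI". The same section asks for data from exposed controls in order to "develop refined algorithms incorporating drug-related factors, host genetic and environmental risk factors".

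Protocol, Proposal Aims: the hypothesis is that "the severity of DILI is determined by factors that modulate cellular response to oxidative stress". The marker panel is meant to reflect the balance "between pro- and anti-inflammatory responses to oxidative stress. So, we will develop a panel of markers that assess the severity of DILI".

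Protocol, Healthy Control Group: "Adults who are exposed to the same drugs (as those responsible for DILI) without developing DILI will be identified". They are found through hospital pharmacy databases and through website and social-media advertising. The Enrolment section also allows untreated controls. A second comparator, the symptomatic controls, consists of suspected cases later found to have another explanation.

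Protocol, Appendix 1: Visit 1 records demography, co-morbidity, alcohol, "Smoking history" and "Body height and weight". The Data collection section says controls follow the same collection, apart from information about a DILI episode. A footnote to Appendix 1 says control groups have one visit and no clinical blood tests.

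**The concern.** A factor that influences the marker and also differs between cases and controls confounds a raw comparison. The protocol's own Rationale proposes this structure: the named host factors may raise oxidative stress, and that stress contributes to DILI. Where a candidate marker responds to oxidative stress, a t-test or rank test cannot separate the effect of DILI from the effect of being, for example, older or a smoker.

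No design step balances these factors for the non-symptomatic controls. They are chosen by drug exposure alone, or may be untreated. Blinding the laboratory protects against assessment bias, not against confounding. The bias does not shrink with recruitment; a larger sample makes a spurious difference more likely to reach significance. The Rationale also says the consortium wants data that support regulatory qualification of biomarkers, so a list of candidates that partly reflects host differences would be costly to follow up.

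**Working it through.** **No figure to reproduce.** The Study Summary gives the sample size estimate as not applicable. No alpha, power, effect size or SD is stated, so what follows is illustration only.

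**Inputs from the protocol.** 300 confirmed cases among 430 suspected cases (Primary endpoint), which implies 430 − 300 = 130 symptomatic non-DILI controls.

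**Assumed inputs.** 300 non-symptomatic controls, because the text at hand states no target for them; a two-sided 5% test; a marker with no true DILI effect and SD 1; and the host imbalances below.

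**Step 1: size of a spurious difference.** If a host factor differs by d SD between groups and correlates r with the marker, the raw difference is biased by r × d.
- Mild: r = 0.2, d = 0.3 gives 0.06 SD.
- Strong: cases 10 years older (SD 15) with marker–age correlation 0.2, plus metabolic syndrome in 40% against 25% with a 0.5 SD marker shift. The sum is 0.2 × 10/15 + 0.5 × (0.40 − 0.25) = 0.133 + 0.075 = 0.208 SD, rounded to 0.2. Adding the two terms overstates the bias if part of the age correlation runs through metabolic syndrome.

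**Step 2: chance that the null marker is significant.** With bias b, the rejection rate is P(|Z + b/se| > 1.96), where se = √(1/300 + 1/n₂).

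| Assumed bias | 300 v 130 | 300 v 300 |
|---|---|---|
| 0 | 5.0% | 5.0% |
| 0.06 SD | 8.8% | 11.4% |
| 0.1 SD | 15.9% | 23.2% |
| 0.2 SD | 47.8% | 68.8% |

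For the last row, b/se = 0.2 × √(300 × 130/430) = 1.905 and 0.2 × √(300 × 300/600) = 2.449.

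**Step 3: do the rank test or adjustment change this?** Simulation, 3,000 runs per scenario, one host factor:

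| r, d | Sizes | t-test | Mann–Whitney | Regression adjusted for the factor |
|---|---|---|---|---|
| 0.2, 0.3 | 300 v 130 | 8.6% | 8.5% | 4.7% |
| 0.3, 0.5 | 300 v 130 | 30.0% | 29.1% | 4.4% |
| 0.2, 0.3 | 300 v 300 | 10.7% | 11.1% | 5.0% |
| 0.3, 0.5 | 300 v 300 | 45.5% | 44.0% | 5.5% |

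The non-parametric option is inflated about as much as the t-test. Over all eight simulated scenarios, adjustment gave 4.4% to 6.0%. This holds when the factor is measured and modelled correctly; the simulation does not cover unmeasured factors.

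**The case against.** **A separate analysis plan may add adjustment.** Covariates are commonly left to such a plan, and the protocol sentence does not say that these tests are the sole analysis. This limits the point but does not remove it: the protocol goes beyond silence, naming a method and tying it to the aim of identifying markers, and that method does not serve its own Rationale.

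**Significance is not acceptance.** The Secondary endpoints also provide for evaluating correlation with phenotype and likely diagnostic or prognostic value. A 0.2 SD shift corresponds to an AUC of Φ(0.2/√2), about 0.56, which is almost no diagnostic value. This stands: the percentages above are rates of significance, not rates at which a false marker would be adopted.

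**Symptomatic controls are recruited like cases.** They meet the same inclusion criteria by the same route, so the documents give no reason to expect a host gap as large as the strong scenario. This stands, and the 47.8% for 300 v 130 should not be read as a forecast for that group. Shared drug exposure in hospital patients may also bring some exposed controls closer to cases, though untreated controls and volunteers weaken that.

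**Stronger readings a reader might infer.**
- That oxidative-stress markers will separate the groups only because of host differences. The protocol says these factors may have this effect and gives no data on imbalance, so the documents support only a possible, partial contribution.
- That the comparison sentence is about oxidative-stress markers. It does not mention them, and the panel in Proposal Aims targets severity among cases, which is a different question.
- That every needed covariate is already collected. Appendix 1 has no row for blood pressure, lipids, glucose or waist, and controls have no clinical blood tests. Insulin sensitivity appears in the Study Summary as part of the phenotyping of DILI patients. In controls, metabolic syndrome is available only through reported co-morbidity and BMI.

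**Conclusion.** The point holds in a limited form. The only comparison named is unadjusted, the protocol itself links the host factors to both the biology and the disease, and non-symptomatic controls are not matched on them. A marker could therefore appear to distinguish DILI partly through host differences.

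The size is unknown. The range of about 9% to 69% rests wholly on assumed shifts of 0.06 to 0.2 SD, and its upper end also rests on an assumed 300 non-symptomatic controls. With no imbalance, or no marker–host correlation, the rate stays at 5%. Concern is greatest for drug-exposed or untreated controls and smaller for symptomatic controls. The primary endpoint is unaffected. The change is worth making because it is cheap and brings the analysis into line with the Rationale, not because a large bias has been shown.

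**What to change.** In Statistical Analyses, make the main biomarker comparison a regression of the log or rank-transformed marker on study group, adjusted for age, sex, BMI, smoking, alcohol and reported metabolic co-morbidity from Visit 1. Report it separately for cases against non-symptomatic controls and for cases against symptomatic controls. Keep the raw t-test or rank test as descriptive.

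The cost is a wording change and a few degrees of freedom: six covariates if each enters as a single term, against 430 participants in the comparison with symptomatic controls. No new data are needed for this model. Residual confounding by metabolic syndrome will remain, because it cannot be established by blood test in single-visit controls, and the report should say so.

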Case of need: One of the biggest hurdles in DILI studies is the limited number of identified cases. Due to the relative rarity of this condition it is unlikely that a single hospital will be able to identify a sufficient number of cases to perform well-powered studies. Hence, a collaborative effort is practically a prerequisite for these kinds of studies. National multicentric DILI registers, such as the Spanish DILI Registry and the US Drug-induced liver injury network (DILIN) have demonstrated the advantage of collaborations [6,7]. Furthermore, international consortia, such as SAFE-T (www.imi-safe-t.eu) and iDILIC / iSAEC (www.saeconsotrium.org) have also emerged with the goal of developing new more sensitive and specific DILI markers than the routine liver profile markers currently used in clinical practice to determine liver injury, as well as genetic variations that can predict DILI susceptibility.

To address this challenge, the Pro Euro DILI consortium of leading European research institutions and SMEs has been established.

The consortium will generate exploratory and confirmatory data enabling regulatory qualification of new safety biomarkers for application in drug development.

Given the significant expertise available across the consortium, the group will be able to tackle the key challenges related to successful biomarker qualification. A key driving principle of the consortium is cross-linking via existing networks of top profile research institutions, as well as capitalizing on existing data and resources. The Consortium is embedded into a network of international research collaborations such as IMI Transbioline, TransQST, eTRANSAFE, the i2b2 tranSMART Foundation, the CIOMS DILI working group, EPoS, LITMUS, and BBMRI.

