This is a European multicentre collaboration consisting of members of the Pro-Euro-DILI COST Consortium. This is coordinated by 2 centres: The University of Nottingham Nottingham Digestive Diseases Centre (NDDC) within the NIHR Nottingham BRC in the UK. and The Malaga Scientific Research Institute, Spain. Both coordinating centres will be responsible for the adjudication of each potential DILI case entered into the Pro-Euro-DILI Registry database. Both will share responsibility for the overall data monitoring, causality assessment of cases and the organisation/scheduling of regular conference call meetings and annual meetings.

Participating European Centres: (Incl both coordinating centres)

Each Centre will obtain ethical approval for the study, nationally and locally and form links with their local regional liver transplant unit. Each centre will be responsible for the collection of biological samples and the shipment of samples for analysis or storage at Nottingham BRC or Charite, or to an approved research tissue bank for long term storage (when the study ends). Samples will be stored at -80°C and shipped in batches.

Each Centre will also be responsible for entering the corresponding data into the Pro-Euro DILI Registry database (developed by Coresoft Clinic S.L, http://www.coresoft.es), available online. Tutorials on data entry and database implementations will be organized by the co-ordinating centres (Málaga and Nottingham) if required.

The web-based application and data will be hosted at Malaga University servers, with automated data backups on a daily basis, a report system for successful backup monitoring and reliable network connectivity. The software strictly follows the regulations imposed by the European Union ensuring that registries are secure and protected by the law. Furthermore, the software follows the Declaration of Helsinki requirements to ensure protection of patient's rights. No data that can reveal the patients identity will be entered into the database. Internet access to the registry platform is password protected and all stored passwords will be encrypted. Subsequent transfer of datasets for analysis will follow agreed data transfer procedure and adhere to data protection standards.

Collaborating centres include (but will not be limited to):

Primary endpoint

Acquisition of clinical samples and clinical data collected from a total of (across all sites in Europe):

430 suspected DILI cases (symptomatic)

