 Of which 300 confirmed DILI cases

Secondary endpoints

We will collate detailed and comprehensive data using an electronic case report form (eCRF) to achieve in-depth phenotyping. (A paper version for data collection is available as a separate document: Annex. 1 CRF.)

Levels of putative biomarkers in samples will be assessed and evaluated to determine correlation with diseases phenotype and likely value in diagnosis or prognosis.

Causality assessment: Causal relationships between the event and the drug will be assessed using the Roussel Uclaf Causality Assessment/Council of International Organization of Medical Sciences (RUCAM/CIOMS). DILI will be phenotyped and severity graded as recommended by the phenotyping standardization project [4].

Standard variables in DILI, such as type of liver damage, severity and chronicity, will be classified as recommended by the phenotyping standardisation project [4]. The type of liver damage will be defined as hepatocellular, cholestatic or mixed based on the ratio (R) between alanine transaminase (ALT) and alkaline phosphatase (ALP) expressed in times the upper limit of normal (ULN), R = (ALT/ULN) / (ALP/ULN). Hepatocellular damage is defined as R≥5, cholestatic damage ≤2 and mixed damage as 2<R<5. The R value will be calculated from the first available analytical values after DILI initiation.

Severity of DILI will be graded as follows:

Mild: Elevated ALT/ALP concentration reaching criteria for DILI but total bilirubin (TBL) concentration <2x ULN

Moderate: Elevated ALT/ALP concentration reaching criteria for DILI and TBL ≥2x ULN, or symptomatic hepatitis

Severe: Elevated ALT/ALP concentration reaching criteria for DILI, TBL ≥2x ULN and one of the following:

• international normalized ratio (INR) ≥1.5

Pro-Euro-DILI Registry Protocol Page 11 of 32

- ascites and/or encephalopathy, disease duration <26 weeks and absence of underlying cirrhosis
- other organ failure considered to be due to DILI

Fatal or transplantation: Death or liver transplantation due to DILI

Disease duration will be graded as follows:

• **Persistent DILI:** Evidence of continued liver injury >3 months for hepatocellular or mixed type of liver damage and >6 months for cholestatic liver damage

• Chronic DILI: Evidence of persistent liver injury at >1 year after the onset of DILI

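### Group tests are named as the way to find markers that distinguish DILI, but a significant group difference does not show the diagnostic or prognostic value that the secondary endpoint asks for

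*Protocol*

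**What the plan says.** The method and its purpose stand in one sentence (Protocol, Statistics and Data Analysis, Statistical Analyses). The method is a comparison of study groups by t-tests and non-parametric tests, and the purpose is "to identify biomarkers which distinguish DILI". No measure of discrimination is named there, and no significance level.

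Under Secondary endpoints, marker levels are to be related to phenotype and judged for "likely value in diagnosis or prognosis". 

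The primary endpoint is the collection of samples and data from 430 suspected cases across Europe, "Of which 300 confirmed DILI cases". Enrolled patients who turn out to have another explanation for their illness stay in the study, "termed 'symptomatic controls' for analysis purposes" (Protocol, Healthy Control Group). The protocol states no number for that group. The Study Summary lists the sample size estimate as not applicable.

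**The concern.** The endpoint asks whether a marker helps to classify or predict in an individual patient. The stated method asks whether two groups differ in mean or rank. With a few hundred patients the second question can be answered yes when the answer to the first is close to no.

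The protocol's own rationale draws this distinction. It notes that known HLA associations with DILI have seen little clinical use because their positive predictive value is low. Yet the Statistical Analyses sentence makes association the step that identifies a distinguishing marker.

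At stake is how the secondary biomarker results are read. If significance is the criterion, weak markers and strong ones carry the same label, and nothing in the stated output tells them apart.

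**Working it through.** The protocol has no power or sample size calculation, so there is no figure of its own to reproduce. The check asks how small an observed separation would already be significant.

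**Inputs**
- Confirmed DILI: 300 (Primary endpoint).
- Symptomatic non-DILI: 430 − 300 = 130 at most (derived, not stated).
- Two-sided 0.05, one marker, normally distributed with equal SDs (all assumed).

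**Smallest significant difference, 300 v 130**
- SE of the standardised difference = √(1/300 + 1/130) = 0.105.
- Critical d = t(0.975; 428 df) × SE = 1.966 × 0.105 = 0.206.
- AUC = Φ(d/√2) = Φ(0.206/1.414) = 0.558.
- Sensitivity at 90% specificity = Φ(0.206 − 1.282) = 0.141.
- Cross-check with the rank-sum test: null SE of the AUC = √[(300 + 130 + 1)/(12 × 300 × 130)] = 0.0303, so the threshold is 0.5 + 1.96 × 0.0303 = 0.559. Both types of test give the same answer.

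**Observed versus true AUC**
- A true AUC of 0.56 means d = √2 × Φ⁻¹(0.56) = 0.2135.
- Power ≈ Φ(0.2135/0.105 − 1.96) = 0.53.
- 80% power needs a true AUC of about 0.58.

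**Threshold under other groupings (same formula)**

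| Comparison | Source of numbers | Observed AUC at p = 0.05 |
|---|---|---|
| 300 v 300 | control number assumed | 0.55 |
| 300 v 130 | European totals, subtraction | 0.56 |
| 50 v 100 | UK: 150 suspected, 50 confirmed | 0.60 |
| 300 v 20 | all confirmed v UK autoimmune hepatitis | 0.63 |
| 50 v 20 | UK confirmed v UK autoimmune hepatitis | 0.65 |

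**Would a multiplicity correction cure it?** The number of markers is not given, so a range is shown. At 300 v 130, Bonferroni for 20, 100 or 1,000 markers gives critical d = 0.319, 0.368 or 0.430, that is AUC 0.59, 0.60 or 0.62. Sensitivity at 90% specificity is then only 17% to 20%. A stricter level guards against chance findings but does not turn significance into a measure of discrimination.

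**What the same patients give if the AUC is estimated (Hanley–McNeil, 300 v 130)**
- At AUC = 0.80: Q₁ = 0.80/1.20 = 0.667 and Q₂ = 2 × 0.64/1.80 = 0.711.
- Variance = [0.16 + 299 × (0.667 − 0.64) + 129 × (0.711 − 0.64)]/(300 × 130) = 0.000444, with Q₁ and Q₂ unrounded. SE = 0.0211 and half-width = 0.041.
- 95% CIs: observed 0.56 gives 0.50 to 0.62; 0.70 gives 0.65 to 0.75; 0.80 gives 0.76 to 0.84; 0.90 gives 0.87 to 0.93.

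A marker at 0.56 and one at 0.80 are both significant, but their intervals do not overlap. The limit lies in the measure chosen, not in the number of patients.

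**The case against.** The strongest reply is that one sentence in a registry protocol is not the whole plan. A statistical analysis plan, not shown here, may add ROC curves or models. The sentence does not say that p < 0.05 selects a marker, and the Secondary endpoints section promises an evaluation that goes beyond a group test. The primary aim is to build a sample and data resource, so a weak screening test spoils nothing that is stored. This stands as a limit on importance. It does not remove the mismatch: the protocol ties a named method to a named purpose, and the method does not measure what the endpoint asks.

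A reader might infer four stronger points. The document does not support them.

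- *That the analysis cannot show diagnostic value.* The sentence also names non-parametric tests. If that means the rank-sum test, its statistic divided by n₁n₂ is the AUC. The p-value does not show diagnostic value, but an AUC could be read from the same test. The protocol just does not say that it will be.
- *That running two tests inflates the false positive rate.* Nowhere does the text say that both are run on each marker, or that either result is accepted. Choosing one or the other by distribution is at least as natural a reading.
- *That one cohort serves for both discovery and confirmation.* The statement is made of the consortium: "The consortium will generate exploratory and confirmatory data enabling regulatory qualification of new safety biomarkers for application in drug development". The same section sets the consortium within a wider network that draws on existing data. The Outline of Laboratory Analyses says that stored plasma and serum will be used for markers found in other studies, and that later studies can use the resource for validation.
- *That the promised panel cannot be built.* The Proposal Aims say "So, we will develop a panel of markers that assess the severity of DILI". That is a separate aim about severity among cases. The 300 v 130 comparison does not bear on it, and how such a panel is modelled can be left to an analysis plan.

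**Conclusion.** The concern holds as a mismatch between a stated method and a stated endpoint. Significance in a group comparison should not be what makes a marker one that distinguishes DILI. At 300 v 130 an observed AUC of about 0.56 suffices, and across the groupings considered the threshold stays between about 0.55 and 0.65.

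The figures rest on an assumed two-sided 0.05, on equal-variance normal markers, and on a comparator number obtained by subtraction. They illustrate the problem and do not forecast what the study will report. It would be wrong to read them as saying that a marker with a true AUC of 0.56 will be declared significant, because its power is only about 53%.

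The point touches a secondary endpoint and leaves the primary endpoint, the collection of samples and data, unaffected. It is worth acting on because a better measure is available from the same patients at almost no cost.

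**What to change.** Reword the sentence in Statistical Analyses along these lines: for each marker, the main measure is the AUC with 95% CI for confirmed DILI versus symptomatic non-DILI, on Visit 1 samples, reported alongside the gain in AUC over ALT, ALP and bilirubin; t-tests and rank tests are descriptive.

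The three routine tests are already obtained at Visit 1 for suspected cases, because the eligibility thresholds use them. They are not available for the single-visit control groups, for whom Appendix 1 says clinical blood tests are not done. That is a further reason to base the main comparison on the symptomatic group. Since entry is selected on these tests, the gain applies to patients who meet the thresholds.

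The cost is a protocol wording change and modest programming. No extra visits, samples or patients are needed. A split of the cohort into selection and confirmation parts is not asked for. Halving both groups would widen the interval at AUC 0.80 from about ±0.04 to about ±0.06 (0.041 × √2 = 0.058), and whether that is worth paying is for the analysis plan.
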